Evidence that the toxicity rate is excessive will be considered sufficient if the lower limits of the 90% one-sided confidence intervals for the estimates of the true toxicity rates exceed the toxicity limits defined above (i.e., 20% for Grade 3 events and 10% for Grade 4 events), after the first 5 patients have been accrued. Operationally, this will occur if any of the following events occurs within a study arm: Grade ≥ 3 events (or Grade >1 autoimmune events) are present in at least 3 out of 5, 4 out of 9 (or less), 5 out of 13 (or less), or 6 out of 15 (or less) of the subjects accrued (within a study arm). Furthermore, accrual will be temporarily suspended if any of the following events occur: Grade 4 events are present in at least 2 out of 5, 3 out of 11 (or less), or 4 out of 15 (or less) of the subjects accrued (within a study arm).

If one of these thresholds is reached, accrual will be temporarily suspended and the study will be reviewed by the UW DSMC (data and safety monitoring committee) to consider safety and dose modifications with respect to treatment arm. Once the study is suspended, it would only be reopened if modifications could be made, and approved by the DSMC and the UW-IRB, to assure that patient safety is reestablished. If not, the study would be closed.

B. Endpoints

Patients will come off study at the time of radiographic disease progression, with progression being defined only AFTER the first 3-month staging evaluation, at the time of undue toxicity (as defined below), or at the discretion of the patient and treating physician that other therapies for prostate cancer are warranted. Patients should be discouraged from discontinuing protocol treatment for PSA rise only. Patients will continue to have blood drawn for immune studies, as per study calendar, up to one year after screening, even if off study prior to that time. The 6 month visit, in particular, is important to collect for the purpose of endpoint analysis. Subjects who have not come off study earlier for these reasons will come off study at the end of the one-year treatment period.

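### The Grade 3 toxicity list omits 3 of 6 patients, which meets the protocol's own confidence-limit criterion

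*Combined protocol and SAP*

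**What the plan says.** Section 6.A (Study Arm Assignment and Toxicity Assessment) sets limits of "20% for Grade 3 events and 10% for Grade 4 events". The Grade 3 limit also covers autoimmune events above Grade 1. Evidence of excess toxicity is sufficient when "lower limits of the 90% one-sided confidence intervals for the estimates of the true toxicity rates exceed the toxicity limits defined above", assessed "after the first 5 patients have been accrued".

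The section then gives the working form of the rule: "Operationally, this will occur if any of the following events occurs within a study arm". For Grade 3 or worse events the counts begin "at least 3 out of 5, 4 out of 9 (or less), 5 out of 13 (or less"), and the last entry is six events among 15 or fewer patients. For Grade 4 events they are "at least 2 out of 5, 3 out of 11 (or less), or 4 out of 15 (or less").

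Reaching any of these counts suspends accrual temporarily and sends the study to the data and safety monitoring committee. Section 12.F plans 15 patients per arm. The protocol does not name the confidence-interval method.

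**The concern.** The list is presented as the criterion in countable form, so the two should agree at every number of patients from 5 to 15. The Grade 3 entry for five patients stands for five only, and the next entry requires four events for any number from six to nine. Three events in six patients therefore do not trigger the list. If the lower limit for 3 of 6 is above 20%, the same paragraph gives two answers for the same data.

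Staff will count events against the list rather than compute confidence limits. When half of an arm's first six patients have related Grade 3 or worse events, the criterion calls for suspension and review, while the list contains no trigger. Section 15.A.1 acknowledges that boosting with a second vaccine against the same antigen could cause more autoimmune events than either vaccine alone, so an early cluster is what this rule is meant to catch.

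**Working it through.** **Inputs (section 6.A; arm size from 12.F).** One-sided 90% lower limit; thresholds 0.20 (Grade 3 or worse) and 0.10 (Grade 4); assessment from n = 5 to n = 15.

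**Formula.** The exact (Clopper-Pearson) lower limit for x events in n patients exceeds p0 exactly when P(X ≥ x | n, p0) < 0.10. The limit itself is the 10th percentile of a Beta(x, n − x + 1) distribution.

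**Reproducing the Grade 4 list (p0 = 0.10).**

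| x/n | Tail probability | Lower limit | Criterion met | On list |
|---|---|---|---|---|
| 2/5 | 0.0815 | 0.1122 | yes | yes |
| 2/6 | 0.1143 | 0.0926 | no | no |
| 3/11 | 0.0896 | 0.1048 | yes | yes |
| 3/12 | 0.1109 | 0.0957 | no | no |
| 4/15 | 0.0556 | 0.1218 | yes | yes |

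The exact method returns the Grade 4 list at every n from 5 to 15.

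**The Grade 3 list (p0 = 0.20).**

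| x/n | Tail probability | Lower limit | Criterion met | On list |
|---|---|---|---|---|
| 3/5 | 0.0579 | 0.2466 | yes | yes |
| **3/6** | **0.0989** | **0.2009** | **yes** | **no** |
| 3/7 | 0.1480 | 0.1696 | no | no |
| 4/9 | 0.0856 | 0.2104 | yes | yes |
| 4/10 | 0.1209 | 0.1876 | no | no |
| 5/13 | 0.0991 | 0.2005 | yes | yes |
| 5/14 | 0.1298 | 0.1851 | no | no |
| 6/15 | 0.0611 | 0.2256 | yes | yes |

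For 3/6 by hand: P(X ≥ 3 | 6, 0.20) = 20(0.2³)(0.8³) + 15(0.2⁴)(0.8²) + 6(0.2⁵)(0.8) + 0.2⁶ = 0.08192 + 0.01536 + 0.00154 + 0.00006 = 0.0989, which is below 0.10. Across n = 5 to 15 the only mismatch is at n = 6.

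**Other interval methods.** Wilson, Wilson with continuity correction, Wald, Jeffreys, Agresti-Coull and mid-P limits all put 3/6 above 20%. It falls below only with continuity-corrected Wald limits or exact 95% limits. Both of those contradict other entries; for example, each would require 5 events at n = 9, where the list says 4. None of the methods tried reproduces the full Grade 3 list.

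**Size.** The state is reached by two events in the first five patients and one in the sixth, with probability C(5,2)p²(1 − p)³ × p = 10p³(1 − p)³. From there, an exact recursion follows the list to n = 15, taking each patient's outcome as known before the next enrols.

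| True rate | Reach 3/6 with no earlier trigger | Further patients enrolled from there, mean | Suspension by n = 15, list | Suspension by n = 15, list with 3/6 |
|---|---|---|---|---|
| 20% | 4.1% | – | 14.8% | 16.5% |
| 30% | 9.3% | 3.9 | 42.4% | 44.3% |
| 40% | 13.8% | 2.9 | 71.6% | 72.9% |
| 50% | 15.6% | 2.2 | 90.5% | 91.0% |

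At a true rate of 30%, an arm that has reached 3/6 never triggers the list later in 21% of cases. Averaged over all arms, the extra enrolment is 0.093 × 3.9 = 0.36 patients at 30%, 0.138 × 2.9 = 0.40 at 40%, and 0.156 × 2.2 = 0.34 at 50%.

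**The case against.** The arithmetic is not in dispute; the case on the other side is about weight.

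- **The overall effect is small.** The chance of suspension changes by no more than about 2 percentage points at the rates examined, and by 1.3 points at a clearly toxic 40%. This stands. One cell is wrong, and the rule as a whole still works.
- **The sequential figures are idealised.** Arm 2 dosing runs to month 9, section 8 counts toxicity to one month after the last immunization, and section 12.F plans 30 patients in 18 months. A third event may first be known when more than six patients are enrolled, and 3 of 7 does not meet the criterion. This stands as a limit on the size estimates. It does not alter the mismatch at n = 6.
- **Other safeguards exist.** The criterion itself stays in the text, section 16.B has a working group reviewing adverse events weekly, the monitoring committee reviews serious events, and section 8 holds vaccination after a related Grade 3 event. These reduce the harm, but none of them corrects the list. A missing trigger is also not an instruction to continue.
- **The method is unnamed and the margin is 0.09 percentage points.** That exact limits were used is an inference, though a strong one, since they reproduce every other entry. The thin margin does not excuse the gap, because 5 of 13 clears 20% by only 0.05 points and is listed.

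**Conclusion.** The concern holds. The Grade 3 list departs from the criterion it is meant to implement at one point, n = 6, where the criterion needs three events and the list needs four. This rests on exact one-sided 90% limits, and most common alternatives also place 3 of 6 above 20%.

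The practical effect is modest: a 4% to 16% chance per arm of passing through the unflagged state at true rates of 20% to 50%, and less than half a patient of extra enrolment per arm on average at 30% to 50%. Those sizes assume that outcomes are known at once. The point does not touch the primary endpoint, the sample size or the efficacy analysis. It should still be corrected, because it is a safety threshold that is wrong as written and the correction is trivial.

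**What to change.** In section 6.A, replace the first Grade 3 entry (3 out of 5) with 3 out of 6 or fewer, keeping the start at five patients. The remaining Grade 3 entries and the Grade 4 list stay as they are. Naming the exact (Clopper-Pearson) method in the same sentence would let anyone check the counts. If the sponsor prefers the present list, the criterion must be restated so that the list follows from it.

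The change is one entry in the protocol text. Its cost is more suspension when the true rate is exactly 20%: 16.5% instead of 14.8% per arm, or 1.7 percentage points. A suspension is temporary pending committee review.

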 pTVG-HP (100 μ g) with rhGM-CSF (208 μ g) administered intradermally (i.d.) biweekly 4 times, then every 3 months to complete a 1-year treatment period (i.e. weeks 6 (day 43), 8 (day 57), 10 (day 71), 12 (month 3), then months 6 and 9)

A. **Study Arm Assignment and Toxicity Assessment**

Patients with asymptomatic-to-minimally-symptomatic, castrate-resistant, metastatic prostate cancer, with evidence of progressive disease, and a calculable PSA doubling time with at least 3 serum PSA values collected over a minimum of 3 months, will be invited to participate. These are subjects who would be eligible to receive sipuleucel-T as routine standard of clinical care. Subjects will be randomly assigned to a treatment group, stratified by pre-treatment estimated survival (< 18 months, ≥ 18 months), using the Halabi nomogram [50], and using laboratory/clinical data collected at screening for this determination. This stratification was chosen given the identification in a previous clinical trial that patients with more indolent disease characteristics appeared to have a greater benefit from vaccine treatment in terms of overall

survival, and the specific use of an 18-month cutoff is currently being used in prospective evaluation of other vaccine trials [51]. Given the absence of significant adverse events observed in previous clinical trials with either sipuleucel-T or pTVG-HP, no adverse events > grade 2 are anticipated. However, all study patients will be evaluated for evidence of toxicity, and further accrual to either treatment arm will be discontinued if the toxicity rate is deemed to be excessive. A toxicity rate of 20% for Grade 3 events (or Grade > 1 autoimmune events) or 10% Grade 4 events given an attribution of at least possibly related to study treatment will be considered excessive. Grade 3 limited site reactions (lasting < 48 hours) and fevers/chills (lasting < 48 hours) will be excluded from this assessment as expected possible adverse events of limited duration.

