A difference in the immune response rate of 55% between the two arms will be detected with at least 84% power. Analogously, a difference in the efficacy response rate of only 40% between the two arms will be detected with 53% power at the one-sided 5% significance level. In order to account for unevaluable patients, 30 eligible patients (15 per arm) will be accrued and randomized. Based on past experience with this patient population treated at our institution, we anticipate that the proposed total number of 30 patients will be accrued within 18 months. Each patient will be followed for at least 12 months.

G. Statistical Analysis Plan

G.1. General

This section outlines the statistical analysis strategy and procedures for the study. If after the study has begun changes are made to primary and/or key secondary objectives, or the statistical methods related to those objectives, then the protocol will be amended.

Summary tabulations will be presented that will display the number of observations, mean, standard deviation, median, range, minimum, and maximum for continuous variables and the number and percent per category for ordinal and categorical data. All endpoints of this study will be presented graphically where possible using boxplots and histograms for continuous variables and (stacked) bar charts for categorical variables. Data analysis will be performed using SAS[®] (SAS Institute Inc., Cary, North Carolina) version 9.2 or greater.

There are many comparisons made between the two trial arms for multiple measurements, both clinical and laboratory. However, since this a pilot study, no adjustment will be made for

multiple comparisons. Except for the primary immunological endpoint, where the comparison between arms will be conducted at the one-sided 0.05 significance level, all other comparisons will be made using a two-sided test at a significance level of 0.05 without adjustment for multiplicity.

G.2. Baseline Comparability

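### The toxicity suspension rule in Section 6.A counts events against all subjects accrued, so Arm 2 patients awaiting their first DNA dose dilute vaccine toxicity, and the rule can fire late and occasionally not at all

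*Combined protocol and SAP*

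**What the plan says.** Section 6.A calls toxicity excessive when the "lower limits of the 90% one-sided confidence intervals for the estimates of the true toxicity rates exceed the toxicity limits defined above", with limits of "20% for Grade 3 events and 10% for Grade 4 events". It turns this into counts per arm. Grade 3 or higher events (or autoimmune events above Grade 1) trigger suspension if they "are present in at least 3 out of 5, 4 out of 9 (or less"), with further steps at "5 out of 13 (or less), or 6 out of 15 (or less) of the subjects accrued (within a study arm"). The second list reads "Grade 4 events are present in at least 2 out of 5, 3 out of 11 (or less"), then 4 of 15. The rule starts once five patients have been accrued. Events count if they are at least possibly related to study treatment, so in Arm 2 sipuleucel-T and vaccine events are pooled.

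Section 6 gives the DNA doses at "weeks 6 (day 43), 8 (day 57), 10 (day 71), 12 (month 3), then months 6 and 9". Section 9.B places randomization at screening, within two weeks before day 1. Section 12.F plans 15 patients per arm and says "we anticipate that the proposed total number of 30 patients will be accrued within 18 months". Sections 6.A, 8, 12 and 14 contain no requirement that a counted subject has received a DNA dose or been observed for any period.

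**The concern.** A confidence limit for a toxicity rate assumes that all n patients in the denominator were at risk of the event. For vaccine toxicity in Arm 2 this fails while accrual is open. A patient is counted from randomization but cannot have a vaccine event until day 43 at the earliest, and a patient who leaves before day 43 stays in the denominator for good. The 20% and 10% limits are then not the limits actually applied to vaccine toxicity.

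This matters most in Arm 2. Section 15.A.1 itself raises the possibility that priming and boosting against the same antigen could produce more autoimmune events than either treatment alone. The rule acts by suspending accrual. Once all 15 patients are vaccinated the two denominators agree, but by then there is no accrual left to suspend.

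**Working it through.** **1. Reproduce the plan's boundaries.** The exact one-sided 90% lower limit for x events in n patients is the 10th percentile of a Beta(x, n − x + 1) distribution.

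| Rule | Listed boundary: lower limit | Same x, larger n: lower limit |
|---|---|---|
| Grade ≥3, limit 20% | 3/5: 24.7% | 3/6: 20.09%; 3/7: 17.0% |
| | 4/9: 21.0% | 4/10: 18.8% |
| | 5/13: 20.05% | 5/14: 18.5% |
| | 6/15: 22.6% | – |
| Grade 4, limit 10% | 2/5: 11.2% | 2/6: 9.3% |
| | 3/11: 10.5% | 3/12: 9.6% |
| | 4/15: 12.2% | – |

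Every listed boundary satisfies the stated criterion, so the list is an exact binomial calculation on n. The one difference is that 3/6 just exceeds 20% but is not listed. Several boundaries clear their limit narrowly, so one extra patient in the denominator is often enough to miss them.

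**2. Time from randomization to first DNA dose.** Day 1 to day 43 is 42 days. Randomization can precede day 1 by up to 14 days. The lag is therefore 42 to 56 days, or 6 to 8 weeks, before any scheduling delay.

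**3. Patients waiting.** Accrual per arm is 15/18 = 0.83 per month, or 15/(18 × 30.4) per day.
- 42 days: 15/547.2 × 42 = 1.15 patients waiting on average.
- 56 days: 15/547.2 × 56 = 1.54 patients waiting on average.

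If arrivals are Poisson (an assumption), at least one patient is waiting 68% of the time at the shorter lag and 78% at the longer. Two or more are waiting 32% and 45% of the time.

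**4. What this does to a signal.**
- Grade 3: 3 of 5 vaccinated patients meets the boundary. With two waiting, the list sees 3 of 7 (17.0%) and accrual continues. With one waiting it sees 3 of 6, which is not listed.
- Grade 4: 2 of 5 vaccinated meets the boundary. With one waiting, the list sees 2 of 6 (9.3%) and does not fire.

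**5. Chance of suspension before the 15th patient is accrued.** Assumptions: random accrual with a mean gap of 36.5 days, a 56-day lag, vaccine events only, each one day after a randomly chosen dose among the first four, 20,000 simulated trials per rate, Grade ≥3 list.

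| Assumed true rate | Accrued denominator | Vaccinated denominator | Difference |
|---|---|---|---|
| 30% | 26.7% | 33.7% | 7.0 points |
| 40% | 52.5% | 60.6% | 8.1 points |
| 50% | 76.3% | 82.3% | 6.0 points |

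A second simulation used uniform accrual over 18 months with events at the first dose. It gave 30% against 38%, 58% against 65%, and 80% against 85%. For the Grade 4 list it gave 35% against 42% at a 20% true rate, and 65% against 72% at 30%.

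In the same simulation, among trials where the vaccinated version of the Grade ≥3 rule fires, the accrued version fires on the same event in about 45% to 49%, later in 39% to 49%, and never in 2% to 16%. The median delay when late is 31 to 38 days, with about 2 to 2.5 more patients vaccinated.

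**The case against.** The rule monitors study-treatment toxicity by arm, not a vaccine rate alone. Sipuleucel-T infusions start on day 4, so Arm 2 patients are at risk of countable events long before day 43, and those events are diluted much less. This stands, and it limits the point to vaccine events.

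Other safeguards do not use this denominator: individual stopping in Section 8, weekly working-group review in Section 16.B, and committee review of serious events in Section 14. Section 6.A also calls the boundary sufficient evidence, which does not make it the only route to suspension. All of this stands and lowers the stakes.

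The first step could be read as the first five patients in enrolment order, in which case later arrivals would not dilute it. The text neither says nor excludes this, which is a further reason to define the denominator.

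The obvious repair, separate Arm 2 counts by attribution with the same list applied to each, can weaken the rule. Two vaccine events and one sipuleucel-T event in five fully treated patients fire now as 3/5; split, they read 2/5 and 1/5 and neither fires. In simulation, with assumed rates of 30% for vaccine and 10% for sipuleucel-T events, splitting lowers the chance of suspension from 48% to 34%. At 20% and 20% it falls from 47% to 22%. This objection stands in full and shapes the fix.

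A reader might also infer that the rule generally fires late or not at all, or that vaccine toxicity is underestimated at every look. Neither is supported. In about half of the simulated trials where it should fire, both versions fire on the same event. At the 56-day lag no patient is waiting about 22% of the time.

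**Conclusion.** The point holds in a limited form. The list in Section 6.A does not carry out its own criterion for vaccine toxicity in Arm 2 while accrual is open, because it counts patients who cannot yet have had a vaccine event. The rule can therefore fire late, and occasionally not at all.

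The loss is about 6 to 8 percentage points in the chance of suspending before the arm is full. That figure rests on the planned 18-month accrual, a 56-day lag (the upper end of the nominal range), vaccine events only, and assumed true rates of 30% to 50%. A shorter lag makes it smaller; faster accrual or calendar delays make it larger. With accrual in 9 months (an assumption), the accrued version is late in 60% to 77% of the trials where the vaccinated version fires, and never fires in 5% to 24%. The documents do not show that patients would be left unprotected. The correction is worth making because it is cheap and concerns the arm with the untested combination.

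**What to change.** Reconcile the operational list in Section 6.A with its confidence-limit criterion. The denominator, and the five-patient start, should refer to subjects actually exposed to the treatment being assessed, not to all subjects accrued. State the observation window as well: DNA doses run to month 9, so a patient with one dose is only partly observed. Say whether the steps are read in enrolment order.

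Keep the pooled per-arm count of all study-treatment-related events. Any count of vaccine events among vaccinated Arm 2 patients should be added to it. An added count cannot lower the chance of suspension, whereas replacing the pooled count with separate counts by attribution can. The sponsor and the data and safety monitoring committee should set the exact suspension wording.

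The cost is a short amendment to Section 6.A, one extra small count for Arm 2, and a slightly higher chance of a temporary suspension. It needs no data beyond dosing dates.

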An adverse event is defined as any unfavorable and unintended sign (including abnormal laboratory finding unless they are grade 1 and deemed clinically insignificant), symptom or disease temporally associated with a medical treatment or procedure, regardless of whether it is considered related to the treatment or procedure. Note that for this study grade 1 laboratory values deemed clinically insignificant will not be reported as adverse events. Adverse events are categorized as definite, probable, possible, unlikely or unrelated in relation to the medical treatment or procedure performed. A life-threatening event is defined as any adverse event that places the subject, in the view of the investigator, at immediate risk of death from the reaction. All adverse events will be recorded from time of informed consent through 30 days after the final dose of study drug, as well as any time after these 30 days that the event is believed to be at least possibly related to study treatment. Serious adverse events are any events occurring that result in any of the following outcome:

1. Subject death
2. Life-threatening adverse event
3. In patient hospitalization or prolongation of existing hospitalization
4. Persistent or significant disability/incapacity
5. Congenital anomaly or birth defect

Adverse events are classified by organ system and graded by severity according to the current NIH Common Terminology Criteria, as described in Appendix A. The defined grades use the following general guidelines:

- 0 No adverse event or within normal limits
- 1 Mild adverse event
- 2 Moderate adverse event
- 3 Severe adverse event
- 4 Life-threatening or disabling adverse event
- 5 Fatal adverse event

B. Procedure for Reporting Adverse Events

Regulations defining the responsibilities for reporting adverse events are defined by the National Cancer Institute Cancer Therapy Evaluation Program (NCI CTEP, <http://ctep.info.nih.gov>). Please see the details of adverse event reporting in Section 14.C.

Appropriate clinical, diagnostic, and laboratory measures to attempt to delineate the cause of the adverse reaction in question must be performed and the results reported. All tests that reveal an abnormality considered to be drug- or treatment-related will be repeated at appropriate intervals until the course is determined or a return to normal values occurs. Information will be recorded as noted above.

12. Statistical Considerations

A. Overview

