1) Death 2) A life-threatening adverse event 3) An adverse event that results in inpatient hospitalization or prolongation of existing hospitalization for ≥ 24 hours 4) A persistent or significant incapacity or substantial disruption of the ability to conduct normal life functions 5) A congenital anomaly/birth defect. 6) Important Medical Events (IME) that may not result in death, be life threatening, or require hospitalization may be considered serious when, based upon medical judgment, they may jeopardize the patient or subject and may require medical or surgical intervention to prevent one of the outcomes listed in this definition. (FDA, 21 CFR 312.32; ICH E2A and ICH E6).				
Hospitalization	Grade 1 Timeframes	Grade 2 Timeframes	Grade 3 Timeframes	Grade 4 & 5 Timeframes
Resulting in Hospitalization ≥ 24 hrs	10 Calendar Days			24-Hour 5 Calendar Days
Not resulting in Hospitalization ≥ 24 hrs	Not required		10 Calendar Days	
¹ Serious adverse events that occur more than 30 days after the last administration of investigational agent/intervention and have an attribution of possible, probable, or definite require reporting as follows: Expedited 24-hour notification followed by complete report within 5 calendar days for: 
 • All Grade 4, and Grade 5 AEs Expedited 10 calendar day reports for: 
 • Grade 2 adverse events resulting in hospitalization or prolongation of hospitalization • Grade 3 adverse events 				

NOTE: FOR THIS STUDY, GRADE 2 AUTOIMMUNE REACTIONS WILL BE TREATED AS GRADE 3 EVENTS FOR REPORTING PURPOSES.

15. Potential Risks and Benefits, and Procedures to Minimize Risk

A. Potential Risks

A.1. From immunization with DNA plasmid encoding PAP

Two potential toxicities might be predicted to occur from DNA-based vaccines. The first would be immediate toxicity due to the vaccination itself, and a second would be due to immunological

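### The 10% accrual-suspension limit counts Grade 4 events only, so two treatment-related deaths in an arm's first five patients do not trigger it

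*Combined protocol and SAP*

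**What the plan says.** Section 6.A first sets the rates regarded as too high: 20% for Grade 3 events (or autoimmune events above Grade 1) and, for the second limit, "10% Grade 4 events given an attribution of at least possibly related to study treatment will be considered excessive". The evidence is sufficient when the "lower limits of the 90% one-sided confidence intervals for the estimates of the true toxicity rates exceed the toxicity limits defined above", and the limits are then restated as "20% for Grade 3 events and 10% for Grade 4 events), after the first 5 patients have been accrued".

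Two operational lists follow, each applied within an arm:

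- The first counts Grade ≥ 3 events (or autoimmune events above Grade 1). Its cut-offs are 3 of 5, 4 of 9, 5 of 13 and 6 of 15.
- The second is met when "Grade 4 events are present in at least 2 out of 5, 3 out of 11 (or less"); its last step is 4 in 15.

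Reaching either threshold suspends accrual and sends the study to the DSMC. Reopening requires modifications approved by the DSMC and the IRB.

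Section 11.A lists the severity grades separately. Grade 4 is life-threatening or disabling, and the next line reads "5 Fatal adverse event". Expedited Reporting Table D-2 in Section 14 puts Grades 4 and 5 in one column, and its footnote names both: "All Grade 4, and Grade 5 AEs".

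**The concern.** The second limit is the stricter one and is meant for the most severe toxicity. It is stated in three places (the 10% criterion, the parenthesis after the confidence-limit criterion, and the operational list), and all three say Grade 4 alone. The first limit is also loosely called Grade 3 in the narrative, but its operational list corrects this to Grade ≥ 3. The second list has no such correction.

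A related death therefore counts only toward the looser 20% limit, while a life-threatening event that the patient survives counts toward both. The rule is not monotone in severity. If two of the first five patients have Grade 4 events, accrual is suspended. If one of those two events is fatal and is recorded as Grade 5, it is not. The rule exists for unexpected toxicity, and Section 15.A.1 accepts that combining two immunizations against the same antigen could cause more autoimmune events than either alone.

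**Working it through.** **Inputs (Section 6.A).** Limits p0 = 20% and 10%; one-sided 90% lower confidence limit; first list 3/5, 4/9, 5/13, 6/15; second list 2/5, 3/11, 4/15.

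**Step 1: reproduce the plan's cut-offs.** The exact (Clopper-Pearson) lower limit for r events in n patients is the 0.10 quantile of a Beta(r, n − r + 1) distribution. It exceeds p0 exactly when P(X ≥ r | n, p0) < 0.10.

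| Rule | r/n | Lower limit | P(X ≥ r) at p0 |
|---|---|---|---|
| 20% | 3/5 | 24.7% | 0.058 |
| 20% | 4/9 | 21.0% | 0.086 |
| 20% | 5/13 | 20.05% | 0.099 |
| 20% | 6/15 | 22.6% | 0.061 |
| 10% | 2/5 | 11.2% | 0.081 |
| 10% | 3/11 | 10.5% | 0.090 |
| 10% | 4/15 | 12.2% | 0.056 |

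For 2/5 by hand: 1 − 0.9⁵ − 5 × 0.1 × 0.9⁴ = 1 − 0.59049 − 0.32805 = 0.081. At each of the seven stated sample sizes, the stated count is the smallest whose lower limit exceeds p0. The numbers in the plan are right; the problem is which grades are counted.

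**Step 2: apply both lists as written to related deaths.** Assume each fatal event is recorded as Grade 5 only and the arm has no other related Grade ≥ 3 event.

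| Related events in the arm | Second-rule count (needed) | First-rule count (needed) | Suspended? |
|---|---|---|---|
| 2 deaths in 5 | 0 (2) | 2 (3) | No |
| 1 Grade 4 + 1 death in 5 | 1 (2) | 2 (3) | No |
| 3 deaths in 11 | 0 (3) | 3 (5) | No |
| 4 deaths in 15 | 0 (4) | 4 (6) | No |

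Replace each death with a survived Grade 4 event and the second rule is met in all four rows.

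**Step 3: allow for timing.** The lists apply as patients accrue, so in the last two rows early clustering of deaths could already have met the first rule.

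- 3 deaths in 11: all three must fall in the first 5. C(5,3)/C(11,3) = 10/165 = 6% of orderings.
- 4 deaths in 15: at least three must fall in the first 5 (105 arrangements) or all four in the first 9 (126), with 45 counted in both. (105 + 126 − 45)/C(15,4) = 186/1365 = 14% of orderings.

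The two five-patient rows do not depend on order.

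**Step 4: apply the corrected wording.** With Grade ≥ 4 in the second rule, two deaths in five count 2/5. The lower limit of 11.2% exceeds 10%, and accrual is suspended. No cut-off changes, because the 10% limit does not change.

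**The case against.** The strongest reply is that this is a drafting slip. The narrative uses Grade 3 as shorthand for Grade 3 or worse, so Grade 4 beside it presumably means Grade 4 or worse. That reading of intent is probably right, but the operational list restores the sign for one limit and not for the other, and the list is what staff apply.

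It can also be argued that a fatal reaction is usually life-threatening before death and could be counted as Grade 4. With Grade 5 listed separately in Section 11.A, that depends on how the investigator records the event; the plan does not settle it.

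The weightier point is that deaths would not go unnoticed. Under Section 14, Grade 4 and 5 events are reported within 24 hours, the DSMC Chair decides whether immediate action is needed, and the committee can act on significant risk. Section 16.B adds weekly working-group review. This stands as mitigation, so the finding concerns the automatic rule only. All of these routes are discretionary, however, whereas a Section 6.A threshold makes suspension mandatory.

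Finally, related deaths are not expected. Section 6.A anticipates nothing above Grade 2, and the earlier 22-subject trial of this vaccine saw no serious adverse events. Even the corrected rule lets a single related death pass without automatic suspension. Both points are true and limit the practical gain, but neither justifies a weaker rule for fatal events than for survived ones.

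**Conclusion.** The concern holds. As written, two related deaths, or one Grade 4 event and one related death, among the first five patients of an arm do not meet either suspension threshold, although two survived Grade 4 events do. Three deaths in 11 and four in 15 also fail to meet a threshold unless the deaths cluster early (about 6% and 14% of orderings). All three death counts have exact lower limits above the plan's own 10% limit: 11.2%, 10.5% and 12.2%. The conclusion assumes that fatal events are recorded as Grade 5 only and that the arm has no other related Grade ≥ 3 events. Deaths do count toward the 20% rule, and the DSMC can still halt accrual at its discretion. The sponsor should correct this.

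**What to change.** Amend Section 6.A to read Grade ≥ 4 in the three places where the second limit appears: the 10% criterion, the parenthesis after the confidence-limit criterion, and the operational list. This matches the Grade ≥ 3 form of the first list and the pairing of Grades 4 and 5 in Table D-2. The 10% limit and the 2/5, 3/11 and 4/15 cut-offs stay as they are.

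No patients, procedures or analyses are added. The only cost is a slightly higher chance of a temporary suspension, and only when a related death occurs. At a true related Grade ≥ 4 rate of exactly 10%, the corrected rule, checked after each patient from the fifth to the fifteenth, would suspend an arm with probability 13.9%. That is close to the 14.8% for the existing first rule at its own 20% limit.
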